12.7 Interim Analyses and Reporting

There are no plans to conduct an interim analysis.

12.8 Sample Size Justification

Sample size is based upon the following:

- Premarket Notification (510(k)) Guidance Document for Daily Wear Contact Lenses – at least 50 evaluable subjects to be followed for at least 3 months, for claim of substantial equivalence for a lens with different repeating monomer Units (new Parent USAN). In addition, a 2:1 ratio in Test vs Control evaluable subject allocation should be adopted.
- ISO 11980:2012 – 50 completed subjects in Test, for 3 months. Either 2:1 or 1:1 ratio of Test to Control can be accepted.

13 DATA HANDLING AND ADMINISTRATIVE REQUIREMENTS

13.1 Subject Confidentiality

The Investigator must ensure that the subject's anonymity is maintained throughout the course of the study. In particular, the Investigator must keep an enrollment log with

confidential identifying information that corresponds to the subject numbers and initials of each study participant. At the end of the clinical study, the Study Sponsor will collect a copy of the enrollment log *without any identifying subject information*. All documents submitted to the Study Sponsor will identify the subjects exclusively by number and demographic information. No other personally identifying information will be transmitted to the Study Sponsor.

The Study Sponsor may release anonymized study data to external researchers for purposes of future research directly related to the study objectives, or future research that is beyond the scope of the current study objectives. The Informed Consent Form explains this to study subjects. Anonymization means that all identifiable information will be removed from the dataset and all links to the subjects in the study will be removed. Anonymization of the data will maintain confidentiality of the subjects who participate in the study so that they cannot be identified by external researchers. The anonymized data set will contain records from all of the subjects in the current study, but the anonymization process might change the data set in some ways, so external researchers will be informed that they might not be able to duplicate some of the results from this study.

13.2 Completion of Source Documents and Case Report Forms

The nature and location of all source documents will be identified to ensure that original data required to complete the CRFs exist and are accessible for verification by the site monitor, and all discrepancies shall be appropriately documented via the query resolution process. Site monitors are appointed by the Study Sponsor and are independent of study site staff.

If electronic records are maintained, the method of verification must be determined in advance of starting the study.

At a minimum, source documents include the following information for each subject:

- Subject identification (name, sex, race/ethnicity)
- Documentation of subject eligibility
- Date of informed consent
- Dates of visits
- Documentation that protocol specific procedures were performed
- Results of study parameters, as required by the protocol
- IP accountability records

- Documentation of AEs and other safety parameters (if applicable)
- Records regarding medical histories and the use of concomitant therapies prior to and during the study
- Date of study completion and reason for early discontinuation, if applicable

It is required that the author of an entry in the source documents be identifiable. Direct access to source documentation (medical records) must be allowed for the purpose of verifying that the data recorded on the CRF are consistent with the original source data.

Only designated individuals at the site will complete the CRFs. The CRFs must be completed at regular intervals following the clinical study visit schedule. It is expected that all data reported have corresponding entries in the source documents. The Principal Investigator is responsible for reviewing and certifying that the CRFs are accurate and complete. The only subject identifiers recorded on the CRFs will be subject number and subject demographic information.

13.3 Data Review and Clarifications

A review of CRF data to the subject's source data will be completed by the site monitor to ensure completeness and accuracy. After the CRFs have been completed, additional data clarifications and/or additions may be needed as a result of the data cleaning process. Data clarifications are documented and are part of each subject's CRF.

13.4 Sponsor and Monitoring Responsibilities

The Study Sponsor will designate a monitor to conduct the appropriate site visits at the appropriate intervals according to the study monitoring plan. The clinical investigation will be monitored to ensure that the rights and well-being of the subjects are protected, the reported data are accurate, complete, and verifiable from the source documents, and the study is conducted in compliance with the current approved protocol (and amendments[s], if applicable), with current GCP, and with applicable regulatory requirements.

The site may not screen subjects or perform the informed consent process on any subject until it receives a notification from an appropriate Study Sponsor representative that the site may commence conducting study activities. Monitoring will be conducted periodically while the clinical study is ongoing. Monitoring methods may include site visits, telephone, written, and fax correspondence. Close-out visits will take place after the last visit of the last subject at the site.

A Coordinating Investigator may be identified by the Study Sponsor to review and endorse the final study report. In cases where a Coordinating Investigator is engaged, the Study Sponsor will select the Coordinating Investigator based upon their experience, qualifications, active study participation, and their willingness and availability to take on this role.

13.5 Regulatory Documentation and Records Retention

The Investigator is required to maintain up-to-date, complete regulatory documentation as indicated by the Study Sponsor and the Investigator's files will be reviewed as part of the ongoing study monitoring. Financial information is to be kept separately.

Additionally, the Investigator must keep study records and source documents consistent with the terms of the clinical study agreement with the Study Sponsor. If the Investigator retires, relocates, or for any other reason withdraws from responsibility of keeping the study records, then the Study Sponsor must be notified and suitable arrangements made for retention of study records and source documents needed to comply with national and international regulations.

13.6 Quality Assurance and Quality Control

The Study Sponsor will secure agreement from all involved parties to ensure direct access to all study-related sites, source data and documents, and reports for the purpose of monitoring and auditing by the Study Sponsor, and inspection by domestic and foreign regulatory authorities. Quality control will be applied to each stage of data handling to ensure that all data are reliable and have been processed correctly. Agreements made by the Study Sponsor with the Investigator/Institution and any other parties involved in the clinical study will be provided in writing as part of the protocol or as a separate agreement.

14 ETHICS

This clinical study must be conducted in accordance with the ethical principles contained within:

- The Declaration of Helsinki, and in compliance with the ICH E6 GCP Consolidated Guideline, ISO 14155:2011, and the applicable US FDA 21 CFR Regulations.
- SOPs of the Study Sponsor and contract research organizations participating in the conduct of the clinical study and all other applicable regulations.
- Notifications and timelines for reporting protocol deviations should be based upon applicable Ethics Committee requirements.

The Investigator must ensure that all personnel involved in the conduct of the study are qualified to perform their assigned responsibilities through relevant education, training, and experience. The Investigator and all clinical study staff must conduct the clinical study in compliance with the protocol. Deviations from this protocol, regulatory requirements, and/or GCP must be recorded and reported to the Sponsor prior to database lock. If needed, corrective and preventive action should be identified, implemented, and documented within the study records. Use of waivers to deviate from the clinical protocol is prohibited.

Before clinical study initiation, this protocol, the informed consent form, any other written information given to subjects, and any advertisements planned for subject recruitment must be approved by an IRB/IEC. The Investigator must provide documentation of the IRB/IEC approval to the Study Sponsor. The approval must be dated and must identify the applicable protocol, amendments (if any), informed consent form, assent form (if any), all applicable recruiting materials, written information for subject, and subject compensation programs. The IRB/IEC must be provided with a copy of the IB, any periodic safety updates, and all other information as required by local regulation and/or the IRB/IEC. At the end of the study, the Investigator must notify the IRB/IEC about the study's completion. The IRB/IEC also must be notified if the study is terminated prematurely. Finally, the Investigator must report to the IRB/IEC on the progress of the study at intervals stipulated by the IRB/IEC.

Voluntary informed consent must be obtained in writing from every subject and the process shall be documented before any procedure specific to the clinical investigation is applied to the subject. The Investigator must have a defined process for obtaining consent. Specifically, the Investigator, or their delegate, must explain the clinical study to each potential subject and the subject must indicate voluntary consent by signing and dating the approved informed consent form. The subject must be provided an opportunity to ask questions of the Investigator, and if required by local regulation, other qualified personnel. The Investigator must provide the subject with a copy of the consent form written in a language the subject understands. The consent document must meet all applicable local laws and provide subjects with information regarding the purpose, procedures, requirements, and restrictions of the study, along with any known risks and potential benefits associated with the IP and the study, the available compensation, and the established provisions for maintaining confidentiality of personal, protected health information. Subjects will be told about the voluntary nature of participation in the study and must be provided with contact information for the appropriate individuals should questions or concerns arise during the study. The subject also must be told that their records may be accessed by appropriate authorities and Sponsor-designated personnel. The Investigator must keep the original, signed copy of the consent (file in

subject's medical records) and must provide a duplicate copy to each subject according to local regulations.

The Study Sponsor assures that the key design elements of this protocol will be registered on www.clinicaltrials.gov as required by current regulations and, if applicable, other public databases as required by local country regulations. In addition, results of this study will be made publicly available on www.clinicaltrials.gov regardless of outcome as required by current regulations and, if applicable, in other public databases as required by local country regulations.

Short Title:

**Statistical Analysis Plan
CLY935-C010 / NCT04178720**

Full Title:

**Statistical Analysis Plan - US
CLY935-C010**

Protocol Title: Clinical Evaluation of a Daily Wear Monthly Replacement
Silicone Hydrogel Lens

Project Number: [REDACTED]

Reference Number:

Protocol TDOC Number: TDOC-0056910

Author: [REDACTED]
[REDACTED]

Template Version: Version 4.0, approved 16MAR2015

Approvals: See last page for electronic approvals.

Job Notes:

This is the first revision (Version 2.0) of the Statistical Analysis Plan for this study. This version of the Statistical Analysis Plan is based on Version 2.0 of the study protocol.

Executive Summary:

Key Objectives:

The primary objective is to evaluate visual acuity of the investigational [REDACTED] soft contact lens compared to the commercially available BIOFINITY® (Biofinity) soft contact lens.

Decision Criteria for Study Success:

Decision criteria for study success are not applicable for this study.

Table of Contents

Statistical Analysis Plan - US CLY935-C010.....	1
Table of Contents	3
List of Tables.....	4
1 Study Objectives and Design.....	5
1.1 Study Objectives.....	5
1.2 Study Description	5
1.3 Randomization.....	6
1.4 Masking	6
1.5 Interim Analysis.....	6
2 Analysis Sets.....	6
2.1 All Enrolled	6
2.2 Enrolled Dispensed.....	6
2.3 Enrolled Not Dispensed.....	7
2.4 Completed.....	7
2.5 Discontinued.....	7
3 Subject Characteristics and Study Conduct Summaries.....	7
4 Effectiveness Analysis Strategy.....	7
4.1 Effectiveness Endpoints	8
4.2 Effectiveness Hypotheses.....	8
4.3 Statistical Methods for Effectiveness Analyses.....	9
4.3.1 Primary Effectiveness Analyses	9
 	
4.4 Multiplicity Strategy.....	10
4.5 Subgroup Analyses and Effect of Baseline Factors.....	10
4.6 Interim Analysis for Effectiveness	10
5 Safety Analysis Strategy.....	10
5.1 Safety Endpoints.....	10
5.2 Safety Hypotheses	11
5.3 Statistical Methods for Safety Analyses.....	11
5.3.1 Adverse Events.....	11

5.3.2 Biomicroscopy Findings/Slit Lamp Examination 12

5.3.3 Device Deficiencies 12

█ [REDACTED]

█ [REDACTED]

8 Sample Size and Power Calculations 14

9 References 14

10 Revision History 14

11 Appendix 15

List of Tables

Table 1-1 Study Description Summary 5

Table 7-1 Expanded Window 13

Table 11-1 Schedule of Study Procedures and Assessments 15

1 Study Objectives and Design

1.1 Study Objectives

PRIMARY OBJECTIVE

The primary objective is to evaluate visual acuity of the investigational [REDACTED] soft contact lens compared to the commercially available Biofinity soft contact lens.

1.2 Study Description

Key components of the study are summarized in Table 1-1.

Table 1-1 Study Description Summary

Study Design	Prospective, multi-center, randomized, [REDACTED] controlled, double-masked, parallel-group
Study Population	
Volunteer subjects aged 18 or over who are adapted daily wear frequent replacement soft contact lens wearers, excluding Biofinity habitual wearers, have at least 3 months of soft contact lens wearing experience, and who wear their habitual lenses at least 5 days per week and at least 8 hours per day.
 
Subjects must require contact lens correction in a sphere power range from -1.00 to -6.00 D. [REDACTED] [REDACTED] [REDACTED]
 
Target to complete: 90 subjects (60:30; Test:Control) Planned to enroll: ~120 subjects

Number of Sites	~8 (US)
Test Product	[REDACTED] soft contact lenses [REDACTED]
Control Product	CooperVision® BIOFINITY® (comfilcon A) soft contact lenses (Biofinity)
Duration of Treatment	Approximately 3 months
Visits	
Visit 1: Screening/Baseline/Dispense (Day 1) Visit 2: Week 1 Follow-up (Day 8 -2/+2 days) Visit 3: Week 2 Follow-up (Day 15 -3/+3 days) Visit 4: Month 1 Follow-up (Day 30 -3/+5 days) Visit 5: Month 2 Follow-up (Day 60 -3/+5 days) Visit 6: Month 3 Follow-up/Exit (Day 95 -3/+5 days)

1.3 Randomization

A member of the Randomization Programming group at Alcon who is not part of the study team will generate the randomized allocation schedule(s) for study lens assignment.

[REDACTED]

Subjects will be randomized in a 2:1 ratio to receive either [REDACTED] or Biofinity contact lenses, respectively. [REDACTED]

[REDACTED]

[REDACTED]

Randomization schedule will be blocked to ensure a balance (2:1) in lens allocation within sites.

1.4 Masking

This study is double-masked.

[REDACTED]

1.5 Interim Analysis

There are no plans to conduct an interim analysis and no criteria by which the study would be terminated early based upon statistical determination.

2 Analysis Sets

2.1 All Enrolled

All subjects who have signed the informed consent for the study will be included in the All Enrolled analysis set.

2.2 Enrolled Dispensed

Enrolled Dispensed is a subset of All Enrolled subjects/eyes that have been exposed to study lenses. Lenses from the trial fitting set used only for fit, power, and/or visual acuity (VA) determination are not considered study lenses in this context.

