3 PROTOCOL SUMMARY

This will be a prospective, randomized, [REDACTED] controlled, double-masked, parallel-group daily wear clinical study.

Approximately 8 sites in the US will enroll approximately 120 subjects. Subjects will be expected to attend 6 office visits: Screening/Baseline/Dispense, Week 1 Follow-up, Week 2 Follow-up, Month 1 Follow-up, Month 2 Follow-up, and Month 3 Follow-up/Exit. The total expected duration of participation for each subject is approximately 3 months in this daily wear clinical study. Approximately 80 subjects will be assigned to wear the test lenses and 40 subjects will be assigned to wear the control lenses, following the 2:1 subject allocation ratio as recommended by ISO 11980:2012 and the US FDA 510(k) guidance document.

Subjects and the study personnel conducting the study evaluations will be masked to treatment. Subjects who meet the inclusion and exclusion criteria will be randomized to wear either the test contact lenses [REDACTED] in both eyes or the control contact lenses (Biofinity) in both eyes for 3 months of daily wear exposure. Following randomization, subjects will be trial fit in the assigned study lens using the fitting set supplied by the Sponsor, and the overall fit and correct contact lens power for each eye will be determined. [REDACTED]

[REDACTED]
[REDACTED]
[REDACTED]
[REDACTED]

The delegated [REDACTED] staff member will then complete a contact lens order form to obtain lenses for each subject. The Sponsor will send investigational products for each subject to the site after receiving an order from the Investigator.

At the Screening/Baseline/Dispense Visit, study lenses will be dispensed to qualified subjects and the subject will be provided with sufficient lens supplies to follow a monthly replacement schedule until the next visit. All study lenses will be worn for at least 5 days per week and 8 hours per day in a daily wear modality (eg, will not be worn while sleeping). [REDACTED]

[REDACTED]
[REDACTED]

Problem lenses (if any) will not be discarded, but collected by the subject and returned to the investigational site. Regardless of whether the subject is randomized to the test or the control group, CLEAR CARE® Cleaning & Disinfecting Solution (CLEAR CARE) must be used for cleaning and disinfection. [REDACTED]

[REDACTED]
[REDACTED]

[Redacted]

[Redacted]

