10 STUDY PROCEDURES AND ASSESSMENTS

Subjects will be expected to attend 6 office visits, as shown below.

Visit #	Visit Type	Visit Day	Visit Window
Visit 1	Screening/Baseline/Dispense	Day 1	N/A
Visit 2	Week 1 Follow-up Visit	Day 8	Days 6-10
Visit 3	Week 2 Follow-up Visit	Day 15	Days 12-18
Visit 4	Month 1 Follow-up Visit	Day 30	Days 27-35

Visit #	Visit Type	Visit Day	Visit Window
Visit 5	Month 2 Follow-up Visit	Day 60	Days 57–65
Visit 6	Month 3 Follow-up/Exit Visit	Day 95	Days 92–100

Unscheduled Visits and Early Termination Visits are allowed, if necessary.

At the Screening/Baseline/Dispense Visit, following randomization, assigned study lenses will be trial fit using the fitting sets supplied by the Sponsor, and the overall fit and correct contact lens power for the individual subject will be determined. Sites will be provided with an adequate lens supply to dispense the first pair of study lenses during Visit 1 to qualified subjects according to the randomization schedule.

[REDACTED]

At the Screening/Baseline/Dispense Visit, study lenses will be dispensed to the subject. All subjects will wear the study lenses in a daily wear modality, only during waking hours.

Subjects assigned to wearing [REDACTED] or Biofinity contact lenses will insert a new pair of lenses each month and discard them at the end of the month. Problem lenses (if any) will not be discarded, but collected by the subject and returned to the investigational site. [REDACTED]

[REDACTED]

[REDACTED]. VA with study lenses will be measured at all visits, and any decrease of 2 or more lines from the Screening/Baseline/Dispense Visit to any follow-up visit should be explained by the Investigator. [REDACTED]

[REDACTED]

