12 ANALYSIS PLAN

Any deviations to the analysis plan will be updated during the course of the study as part of a protocol amendment or will be detailed in the clinical study report.

All analyses will be conducted according to the applicable statistical analysis plan.

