12.2 Analysis Sets

Five analysis sets will be defined:

- a) All Enrolled – all subjects signing the informed consent form
- b) Enrolled Dispensed – subjects/eyes from All Enrolled that have been exposed to study lenses (not considering trial-fit lenses prior to randomization)
- c) Enrolled Not Dispensed – subjects/eyes from All Enrolled that have not been exposed to study lenses (not considering trial-fit lenses prior to randomization)
- d) Completed – Enrolled Dispensed subjects/eyes completing the study
- e) Discontinued – Enrolled Dispensed subjects/eyes not complete the study

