2.3 Enrolled Not Dispensed

Enrolled Not Dispensed is a subset of All Enrolled subjects/eyes that have not been exposed to study lenses. Lenses from the trial fitting set used only for fit, power, and/or VA determination are not considered study lenses in this context.

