5.3 Statistical Methods for Safety Analyses

5.3.1 Adverse Events

The applicable definition of an AE is in the study protocol. All AEs occurring from when a subject signs informed consent to when a subject exits the study will be accounted for in the reporting. Analysis and presentation of pre-treatment AEs will be separated from treatment-emergent AEs occurring during the study period. A pre-treatment AE is an event that occurs after signing informed consent but prior to exposure to the study lens (not including trial fitting lenses). The period for treatment-emergent AE analysis starts from exposure to study lens until the subject completes or is discontinued from the study.

Descriptive summaries (counts and percentages) for ocular and nonocular AEs will be presented by Medical Dictionary for Regulatory Activities (MedDRA) Preferred Terms (PT). Serious AEs and significant non-serious ocular AEs will be noted. Additionally, relationship to lens will be identified in all AE tables. Unit of presentation for ocular AEs will be eye and nonocular AEs will be subject.

Individual subject listings will be provided for both pre-treatment and treatment-emergent AEs, where any AE leading to study discontinuation will be indicated.

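### Does the differing wording of the trial-fit exclusion in protocol 12.2 and SAP 2.2, 2.3 and 5.3.1 call for a change to the analysis sets or safety tables?

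*SAP*

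**What the plan says.** Protocol 12.2 separates Enrolled Dispensed from Enrolled Not Dispensed by exposure to study lenses, with the qualifier "not considering trial-fit lenses prior to randomization". Protocol section 3 gives the order of events: "Following randomization, subjects will be trial fit in the assigned study lens using the fitting set supplied by the Sponsor". Section 10 repeats it: "following randomization, assigned study lenses will be trial fit using the fitting sets supplied by the Sponsor".

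SAP 2.2 and 2.3 draw the line by purpose, without reference to randomization. In 2.2: "Lenses from the trial fitting set used only for fit, power, and/or visual acuity (VA) determination are not considered study lenses in this context". Section 2.3 repeats this in the same terms. In both documents the Completed and Discontinued sets are subsets of Enrolled Dispensed.

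SAP 5.3.1 defines a pre-treatment adverse event as one after consent and "prior to exposure to the study lens (not including trial fitting lenses". It accounts for all events from consent to exit, presents pre-treatment events apart from treatment-emergent ones, and lists both. SAP 5.3.3 gives a frequency table for treatment-emergent device deficiencies and listings for both kinds. Protocol 12.6 plans a frequency for each deficiency category without that split.

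On precedence, protocol section 12 says: "All analyses will be conducted according to the applicable statistical analysis plan".

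**The concern.** In the visible workflow the trial fit follows randomization and uses the assigned lens. The protocol's qualifier therefore seems to exclude a step that never happens, and the trial fit that does happen would count as exposure. The SAP says the opposite. The same subject can then fall in two different analysis sets, depending on which document the programmer opens.

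There is a safety side too. Under SAP 5.3.1, an event that arises while the randomized lens is on the eye during fitting is labelled pre-treatment. If 5.3.3 follows the same boundary, a deficiency found then is listed but not counted in the frequency table. SAP 5.3.1 also omits the word *only* that limits SAP 2.2, while protocol 9.1 says the first take-home pair comes from the fitting set.

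The trial is wholly descriptive, so the tables by lens group carry the comparison. Misplaced subjects or events would distort the one output on which readers rely.

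**Working it through.** No power or error-rate calculation applies. The check is to follow particular subjects and events through each definition.

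| Case | Protocol 12.2, read literally | SAP |
|---|---|---|
| Randomized, fitted, dispensed | Enrolled Dispensed | Enrolled Dispensed |
| Randomized, fitted, never dispensed | Enrolled Dispensed, then Discontinued | Enrolled Not Dispensed |
| Adverse event during fitting of the assigned lens | After exposure | Pre-treatment; presented separately and listed |
| Defect seen when a pack is opened, before any insertion | Before exposure | Before exposure |
| Defect found with the fitting lens on the eye | After exposure | Pre-treatment if the 5.3.1 boundary applies in 5.3.3; listed |

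**Who is affected.** Set membership differs only for subjects who are randomized, fitted and never dispensed. They cannot be in the Completed set under either wording, so that set and the target of 60 test and 30 control completers (SAP Table 1-1) do not move. The All Enrolled tables do not move either.

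**How large.** The documents give no count of such subjects. The planned assignment is: "Approximately 80 subjects will be assigned to wear the test lenses and 40 subjects will be assigned to wear the control lenses". One subject would be 1/80 = 1.25% of test or 1/40 = 2.5% of control. This shows scale only and is not an estimate; the true number may be zero.

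**Which rule applies.** Protocol 12 hands the analysis to the SAP, so the SAP column is the working rule.

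**Whether that rule is coherent.** It starts exposure at the lens the subject is given to wear, which agrees with the word *Dispensed* in the set names. Nothing in the documents requires the treatment-emergent period to start at the trial fit.

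**Whether events are lost.** They are not. Adverse events are accounted for from consent, and pre-treatment adverse events and deficiencies are both listed. Protocol 11.3 also says that transient lens awareness or visual change during fitting is not an adverse event when the investigator expects it to resolve with adaptation. The affected interval lies within Visit 1.

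**Whether 5.3.1 could reclassify take-home wear.** Only if every lens from the fitting set were treated as a trial fitting lens. Protocol 9.1 calls the dispensed pair study lenses, and SAP 2.2 confines the exclusion to lenses used only for fit, power or acuity. Read together, they leave the take-home pair as study lenses.

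**The case for a change.** The strongest case for a change is that a plan should not leave the start of exposure to inference. Three definitions in three places do so, and aligning them would take a few words. SAP section 5 groups subjects by the lens actually worn, so someone fitted but never dispensed has no clear lens group for the safety tables. No visible output plainly gives, by assigned lens, the reasons for not dispensing or the fitting-period events in those subjects. A small table by assigned lens would need no new assessment, because adverse events, deficiencies and the exit form are already scheduled at Visit 1.

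The wording part stands. Protocol 12.2 does not match the visible workflow or SAP 2.2 and 2.3, 5.3.1 drops a limiting word, and 5.3.3 does not visibly define pre-treatment. But alignment would only restate the rule already in force, and protocol 12 allows deviations from the analysis plan to be detailed in the study report.

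The case for the extra table is weaker. Protocol 10.5.2 counts as discontinued anyone who withdraws or is withdrawn after consent, and protocol 12.5 tabulates incidence and reasons by lens group. SAP section 3 adds a table of reasons, a listing of discontinued subjects and a lens-assignment listing. None is visibly restricted to the Discontinued analysis set, although none expressly includes never-dispensed subjects either. The table could partly repeat these outputs for a group that may be empty. If it started at first insertion, it would also miss defects seen on opening a pack.

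**Conclusion.** The inconsistency is real and is most likely a drafting slip in protocol 12.2. It calls for no change to the plan. One working rule exists because the SAP governs; it is specified in advance and reasonable, and an analyst reading SAP 2.2 beside 5.3.1 would apply it as intended. No effect on any planned result has been shown. There is no hypothesis test of the primary endpoint (protocol 12.4.1.1) and no success criterion (SAP Executive Summary), so no decision can turn on the point.

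The conclusion rests on three assumptions. First, 5.3.3 uses the boundary defined in 5.3.1; this is the natural reading, but the text after 5.3.3 is redacted. Second, few if any subjects are randomized and fitted without being dispensed, a number the documents do not give. Third, the redacted text does not alter the workflow. If it describes a fit before randomization, the protocol's qualifier would have something to refer to, and the SAP would still govern the analysis.
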